1 **Prevalence and determinants of home accidents among Turkish older men and women**

2 **Abstract**

3 **Background:** Home accidents are a significant public health issue in developed and developing
4 countries. The present study aims to identify the factors associated with home accidents among
5 older individuals in Türkiye.

6 **Methods:** Microdata obtained from the Türkiye Health Survey conducted by the Turkish
7 Statistical Institute (TUIK) in 2019 and 2022 were utilized in the present study. Binary logistic
8 regression analysis was used to determine factors influencing home accidents.

9 **Results:**

10 **Conclusion:**

11 **Keywords:** Older individuals, home accident, discrete choice model, binary logistic regression,
12 Türkiye

13

14 **1. Introduction**

15 Home accidents are a significant public health issue in developed and developing countries (1).
16 Home refers to where older individuals spend most of their daily time, thus increasing their
17 likelihood of experiencing any accidents at home. Home accidents are more common among
18 older individuals and can lead to serious health consequences (2). Individuals aged 65 and
19 above are particularly at high risk of home accidents due to physical, psychological, and social
20 impairments. Musculoskeletal problems and sensory and motor function loss in this group
21 increase the risk of accidents (3). Home accidents are assumed to be unintentional and can range
22 from minor injuries to fatalities. These accidents can occur within the home and in surrounding
23 areas such as garages, gardens, terraces, and stairs (4). While unintentional home and

24 recreational injuries pose a risk for individuals aged 85 and older, outdoor injuries also pose a
25 risk for younger, older individuals (aged 75-79) (5).

26 Home accidents represent a significant health problem in terms of morbidity and mortality at
27 older ages (6). The frequency of home accidents is found to be three times higher in women,
28 2.7 times higher in individuals living with children, 2.3 times higher in visually impaired older
29 individuals, and 2.7 times higher in older individuals with poor health status. Moreover,
30 advancing age is considered a risk factor for home accidents (7). Various home accidents
31 include falls, burns, crushes, cuts, and electric shocks (8). Around 80% of injuries that
32 necessitate medical attention take place within the home environment, with a significant portion

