33 of these injuries, approximately two-thirds, being classified as serious injuries, predominantly
34 resulting from falls and burns (5).

35 Similar to the global trend, the older population in Türkiye is rapidly increasing (9). While the
36 global average older population ratio was 9.9% in 2022, Türkiye's older population ratio of
37 9.8% is close to the global average (10). These data indicate that Türkiye has a significantly
38 more ageing population (11). The prevalence of older individuals experiencing at least one
39 accident in Türkiye is 38.6%, with falls being the most common accident at 63.3% (6). As
40 reported in another study, more than half of the older population had experienced a home
41 accident in the previous year (59.4%), with falls (70.2%) and kitchen accidents (31.7%) ranking
42 at the top (12). Epidemiological characteristics of injured patients were examined in Tehran,
43 where traffic accidents and falls were identified as the two most common causes of injury (13).

44 Falls in the home environment account for over 33% of accidents and are the second leading
45 cause of death and the main cause of injury in more than 41.2% of cases. Falls during patient
46 admissions also impose additional burdens and costs on the healthcare system (14). The total
47 medical cost for treating fatal and non-fatal fall injuries in older adults exceeded \$50 billion in
48 the USA in 2015 (15). "Falls" occurring in the bathroom, hallway, living room, or bedroom,

49 originating from the floor or stairs, can result in doctor visits and hospitalizations (1). Factors
50 contributing to increased home injuries include advanced age, economic hardships, obesity, and
51 comorbidities (5). Among older adults living in the community, a significant proportion of falls,
52 ranging from 10% to 38%, lead to non-fatal injuries, hospitalizations, disability, or a decline in
53 independence (16-18). Various risk factors have been identified in association with falls,
54 including advanced age, a history of previous falls, muscle weakness, difficulties with walking
55 and balance, dementia, impaired vision, arthrosis, diabetes, stroke, Parkinson's disease, and
56 urinary incontinence (19).

57 Burns constitute another type of home accident in older individuals. Burn injury is one of the
58 most devastating types of trauma affecting millions of people worldwide, leading to severe
59 morbidity and mortality, with individuals aged 65 and above being the most affected

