60 demographic group. The presence of comorbidities in older individuals leads to higher
61 morbidity and mortality in burns due to age-related changes in the central and peripheral
62 nervous system (20).

63 Older individuals may also experience traumas as a result of accidents that occur within their
64 homes. These traumas can have severe consequences for older adults, leading to increased rates
65 of illness and death (21). The proportion of older individuals presenting to Level I and II trauma
66 centers was 23% in 2003, which increased to 30% in 2009 (22). This rate is expected to reach
67 39% by 2050 (23). The cost of home accidents is estimated to be 3.5 times higher than that of
68 traffic accidents (24).

69 Decreased capacities of older individuals often result in limitations in daily life activities.
70 Ageing and declining individual capacities increase the prevalence of disease and disability
71 among older individuals. Living at home, associated with independence and autonomy-related
72 physical, psychological, and psychosocial benefits, is a desired and essential goal for older
73 individuals (25). Therefore, it is necessary to examine the factors contributing to home

74 accidents among older individuals to ensure home safety. Hence, this study investigates the risk
75 factors affecting home accidents among older individuals in Türkiye.

76 **2. Method**

77 This section will explain the specifics of the data utilized in the research, the variables
78 categorized as dependent and independent, and the methodology employed in the study.

79 **2.1. Data**

80 The research utilised microdata from the Türkiye Health Survey, published by the Turkish
81 Statistical Institute (TUIK) in 2019 and 2022. The most recent data available from TUIK's
82 health survey is 2022. The Türkiye Health Survey is a significant research endeavour that
83 reflects the entire country and enables national and international comparisons. The dataset
84 offers a wide range of health indicators related to the well-being of infants, children, and adults,
85 along with insights into individuals' access to healthcare services (26).

86 **2.2. Outcome Variables**

87 Older individuals are at risk for home accidents due to their developmental characteristics (2,
88 3).

89 The data obtained from individuals aged 60 and above were used in this study. The study's
90 dependent variable is the occurrence of home accidents, measured by the question, "Have you

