91 experienced a home accident resulting in injury in the last 12 months? (Yes, No)." In the
92 established model, the dependent variable categories are assigned 1 if the individual has
93 experienced a home accident and 0 if they have not.

94 **2.3. Independent variables**

95 The independent variables included in the study are those available in the Türkiye Health
96 Survey. These variables were selected as risk factors based on the literature (5, 7, 19, 27-33).

97 The independent variables of this study are gender (female, male), education level (illiterate/less
98 than primary school, primary school, secondary school and above), marital status (single,
99 married), employment status (unemployed, employed), general health status (very good/good,
100 fair, poor/very poor), presence of arthrosis (no, yes), urinary incontinence (no, yes), wearing
101 glasses (yes/cannot see at all, no), experiencing difficulty in carrying or holding items (no
102 difficulty, some difficulty/considerable difficulty/cannot do at all), experiencing difficulty in
103 affording health care services (no, yes), and survey year (2019, 2022).

104 **2.4. Statistical Analysis**

105 Survey statistics in Stata 15 (Stata Corporation) were utilized to address the complex sampling
106 design and weights. Weighted analysis was conducted. Initially, frequencies and percentages
107 were obtained considering the home accident occurrence and years among the older
108 participants. Then, binary logistic regression analyses were employed to identify the risk factors
109 influencing home accidents in older individuals.

110 **3. Results**

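### Does a title naming older men and women oblige the plan to give prevalence and determinants separately by sex?

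*Combined protocol and SAP*

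**What the plan says.** The title is "Prevalence and determinants of home accidents among Turkish older men and women". The written aim at the end of the Introduction is framed without reference to sex: the study investigates the risk "factors affecting home accidents among older individuals in Türkiye". The abstract's aim is likewise about older individuals.

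Section 2.2 (Outcome Variables) defines the outcome as a home accident with injury in the last 12 months, and speaks of one model when it gives the coding: in the "established model, the dependent variable categories are assigned 1 if the individual has" had an accident, and 0 otherwise.

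Section 2.3 (Independent variables) lists eleven variables, with gender first: "The independent variables of this study are gender (female, male), education level (illiterate/less" than primary school, and so on.

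Section 2.4 (Statistical Analysis) uses survey-weighted methods. It describes frequencies and percentages that "were obtained considering the home accident occurrence and years among the older" participants, then regression, where the text runs "participants. Then, binary logistic regression analyses were employed to identify the risk factors". It does not mention gender, confidence intervals, odds ratios, interactions or stratified models.

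**The concern.** A reader of the title could expect two things for each sex: how common home accidents are, and what they are associated with. Section 2.4 promises neither. The descriptive step is organised by accident occurrence and survey year, and no measure of precision is named for any percentage. The regression appears to carry gender as one covariate among eleven, so each other determinant gets one coefficient for both sexes.

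The Introduction adds weight to this. Its background paragraph includes the words "older ages (6). The frequency of home accidents is found to be three times higher in women", so sex is no incidental variable. If arthrosis or incontinence, say, mattered in one sex only, the pooled odds ratio would describe neither sex correctly, and nothing in the written plan would show it.

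**Working it through.** **What there is to reproduce.** The documents state no sample size, event count, significance level or target prevalence for this study, so there is no planned figure to recompute. The check has two parts: a reading of the text, and an illustration of how far a pooled odds ratio could lie from the sex-specific ones.

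**1. Title, aim and analysis side by side**

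| Place | Population named | Sex-specific result promised? |
|---|---|---|
| Title | older men and women | not explicitly; it may simply describe the population |
| Abstract and Introduction (aim) | older individuals | no |
| 2.2 | one model | no |
| 2.3 | gender is a listed variable | no; gender is a covariate |
| 2.4 | older participants / individuals | no; but a gender row is not excluded, and the regression is described in the plural |

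The aim and the analysis agree. Only the title can be read more widely.

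**2. Size of the possible discrepancy (illustration)**

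Inputs from the Introduction: a frequency three times higher in women, and overall prevalences of 38.6% and 59.4% from two cited studies. The first stands in the words "accident in Türkiye is 38.6%, with falls being the most common accident at 63.3% (6). As".

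Assumptions not in the documents: 54% women (range 50% to 56%), 40% exposed in both sexes, the threefold figure read as a ratio of risks, and the sex-specific odds ratios themselves. A low-risk case of 9% in women and 3% in men is also assumed.

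Unexposed risks from an overall value P and a share f of women: men = P / ((1 − f) + 3f); women = 3 × men. With f = 0.54 the denominator is 0.46 + 1.62 = 2.08.

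- P = 38.6%: men 0.386 / 2.08 = 18.6%; women 55.7%.
- P = 59.4%: men 0.594 / 2.08 = 28.6%; women 85.7%.

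The pooled odds ratio is exp(b2) from logit(risk) = b0 + b1·sex + b2·exposure, fitted to the expected cell counts.

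| True OR (women, men) | Risks 9%/3% | 55.7%/18.6% | 85.7%/28.6% | Range with 50–56% women |
|---|---|---|---|---|
| 1.5, 1.0 | 1.380 | 1.298 | 1.164 | 1.12–1.39 |
| 1.0, 2.0 | 1.228 | 1.311 | 1.540 | 1.21–1.64 |
| 1.5, 1.5 | 1.500 | 1.500 | 1.500 | 1.500 |

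In the first row the weight given to women on the log scale is ln(pooled OR) / ln(1.5): 79%, 64% and 37%. The pooled value is a weighted average, as expected. It departs from the sex-specific values only to the extent that one assumes those values differ.

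**3. How relevant the illustration is.** The documents do not describe the 38.6% and 59.4% as limited to accidents with injury, whereas the outcome in section 2.2 is so limited. Combining 59.4% with a threefold ratio implies a sex odds ratio of (0.857 / 0.143) / (0.286 / 0.714) ≈ 15, which is an extreme setting. The ends of the last column, 1.12 and 1.64, come from a still more extreme case: 50% women and P = 59.4%, which gives 89.1% risk in women. These ranges show that the mechanism exists. They do not estimate an error in this study.

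**4. Cost of sex-specific determinants.** Interactions with gender would add 2 (education) + 2 (general health) + 8 (one for each of the other eight two-level variables) = 12 parameters. With no event count given, nobody can say whether the data for men would support them.

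**The case for a change.** The strongest case for a change is that the title and the methods do not match and that closing the gap costs little. Prevalence is the first word of the title, yet no prevalence with an interval is written down, overall or by sex. The gender coefficient gives an adjusted contrast between women and men. It gives no prevalence in either sex and does not show whether the other determinants act alike in both. On the figures above, a pooled odds ratio near 1.3 fits an effect in women only, an effect in men only, or a modest effect in both. The data are already held, so a table and one further model would be quick to produce.

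Much of this stands as description: the items are indeed not written down. It does not show that a planned result would be wrong. The threefold figure is a difference in frequency between the sexes, which the gender term models directly. It is not evidence that arthrosis, education or any other factor acts differently in men and women, and the documents offer no other reason to think so. Without such a reason, the same request could be made for any covariate in the list. The plural wording in section 2.4 and the presence of gender among the study variables also leave room for the very rows and models that are said to be missing.

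**Conclusion.** No change to the plan follows. The point has three parts, and none calls for one.

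- **Title.** It can be read as naming the population. Any mismatch with the aim is a matter of wording.
- **Prevalence by sex with intervals.** This is unwritten reporting detail. Gender is a study variable and the analysis is survey-weighted, so an analyst producing the descriptive table would ordinarily include it, and design-based intervals come from the same survey procedures. Leaving it unsaid makes no planned result unsound.
- **Sex-specific determinants.** This is a fair trade-off. The gain is a check on effect modification for which the documents give no rationale. The price is 12 extra parameters, wider intervals within each sex, more chances of a spurious difference, and an unknown number of accidents among men. Such an analysis would be exploratory and optional.

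The pooled model answers the stated aim. If effects are equal in the two sexes, the pooled odds ratio carries no error (1.50 against a true 1.5). If they differ, it is a weighted average between the two, and its distance from either depends wholly on sex-specific effects that had to be assumed here. The reading of the regression as a single main-effects model is itself an inference, from gender's place in the covariate list and the reference to one model in section 2.2.

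### General health and carrying difficulty are not dated before the 12-month accident outcome, so *determinants*, *influencing* and *affecting* are not supported for these two variables

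*Combined protocol and SAP*

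**What the plan says.** Section 2.2 measures the outcome by one yes/no question, whether the respondent "experienced a home accident resulting in injury in the last 12 months? (Yes, No").

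Section 2.3 lists the predictors by response category. General health is in the line "married), employment status (unemployed, employed), general health status (very good/good" and carrying difficulty in the line "glasses (yes/cannot see at all, no), experiencing difficulty in carrying or holding items (no". Neither has a reference period, an onset date or a qualifier tying it to the time before the accident. The stated basis for the choice is: "Survey. These variables were selected as risk factors based on the literature". Section 2.1 describes survey microdata from 2019 and 2022. It mentions no linkage of respondents between the two years and no pre-accident measurement.

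The wording of the aim varies:
- Title: "Prevalence and determinants of home accidents among Turkish older men and women".
- Abstract, Methods: factors *influencing* accidents.
- Last sentence of the Introduction: risk factors *affecting* accidents.
- Section 2.4: "participants. Then, binary logistic regression analyses were employed to identify the risk factors", continuing "influencing home accidents in older individuals".
- Abstract, Background: *factors associated with* accidents.

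The Introduction supports both directions. It says that a share of falls, "ranging from 10% to 38%, lead to non-fatal injuries, hospitalizations, disability, or a decline in" independence, and that traumas from home accidents raise rates of illness. It also says that accidents are 2.7 times more frequent in older people with poor health.

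**The concern.** A person injured eight months before interview may report poor general health, or trouble carrying things, because of that injury. The model would enter this state as a predictor of the accident. Its odds ratio would then mix any influence of the state on accidents with the effect of the accident on the state, and nothing planned separates the two. With *determinants* in the title and *influencing* in section 2.4, a reader would take the whole odds ratio as influence.

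There is a secondary effect. The odds ratios of other predictors related to these states, such as arthrosis, may depend on whether the states are in the model. The plan gives readers no view of that.

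**Working it through.** The plan states no sample size, number of events, expected odds ratio or prevalence for these variables, so there is no figure to reproduce. The check is textual, followed by an illustration whose inputs are all assumptions.

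**Time order in the text.** The outcome window is the 12 months before interview. The two predictors have response categories only. Selection from the literature explains why they were chosen, but does not date them in these data. Since the Introduction supports both directions, neither can be ruled out.

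**Reverse path alone.** Let *p* be the share with the state before the window, equal in injured and uninjured people (no forward effect). Let *q* be the share of injured people without the state whom the accident moves into it by interview. Then

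prevalence in the injured: p1 = p + (1 − p)q

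apparent OR = [p1/(1 − p1)] / [p/(1 − p)]

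Example: p = 0.20, q = 0.10 gives p1 = 0.20 + 0.80 × 0.10 = 0.28, and OR = (0.28/0.72)/(0.20/0.80) = 0.3889/0.25 = 1.56.

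| Baseline p | q = 2% | q = 5% | q = 10% | q = 20% |
|---|---|---|---|---|
| 20% | 1.10 | 1.26 | 1.56 | 2.25 |
| 30% | 1.07 | 1.18 | 1.37 | 1.83 |
| 60% | 1.03 | 1.09 | 1.19 | 1.42 |

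The 10% to 38% in the Introduction is not used for q. It is a share of falls and combines non-fatal injury, hospitalization, disability and decline in independence.

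**Comparison with the quoted 2.7.** If that frequency ratio is read as an odds ratio (an assumption), the reverse path alone would need q = 25% at p = 20%: the odds become 2.7 × 0.25 = 0.675, so p1 = 0.675/1.675 = 0.403 and q = (0.403 − 0.20)/0.80 = 0.254. At p = 30% it would need 34%. Shifts of 5% to 20% would explain part of such a ratio at most.

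**What a model without the two variables can show.** Population-level logistic fits used arthrosis and one such state. Assumed inputs: arthrosis prevalence 30%; accident risk 10% with neither condition; arthrosis OR 2.00 given the pre-accident state; pre-accident state prevalence 20% without arthrosis and 40% with it.

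| Scenario | Arthrosis OR, state in model | Arthrosis OR, state omitted |
|---|---|---|
| Reverse only (q = 20%) | 1.74 | 2.00 |
| Forward only (state OR 2.7) | 2.00 | 2.42 |
| Both | 1.84 | 2.42 |

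The odds ratio is lower with the state in the model in all three scenarios, so the change between models does not reveal direction. The reduced model recovers 2.00 only when the state has no forward effect.

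**The case against.** **The questionnaire may date the items.** Section 2.3 gives categories, not question wording. This stands as a limit: the supportable statement is that the plan does not report a reference period. If the survey supplies one that settles the order, a sentence in section 2.3 answers the point.

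**The effect may be small.** Carrying difficulty pools some difficulty with worse levels, so a high baseline is plausible. The Introduction says that accidents range upward from minor injuries, so a small lasting shift is plausible too. At a 60% baseline with a 2% shift the apparent odds ratio is only 1.03. This stands, and the range above reflects it.

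**The wording change reaches further than the argument.** An accident cannot change gender or survey year, and almost certainly does not change education at age 60 and above. That is right, and this point makes no claim against those variables. But the title, aim and section 2.4 make one statement about all factors together, and the plan already has a phrase that fits them all. The Introduction sentence on *factors contributing to* accidents is motivation, not a claim from the model, and needs no change.

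**The sensitivity model does not resolve direction.** Correct. It gives no estimate for the two variables, and in two of the three scenarios above the full model is nearer the assumed value. Its use is limited to showing how far the other odds ratios depend on the two variables.

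**Nothing has been interpreted yet.** The abstract's Results and Conclusion are blank and the text ends at the Results heading. The harm is therefore prospective, but the wording can still be settled before anything is reported.

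A reader might go further and infer that these associations are mainly consequences of the accident, or that the two variables should leave the primary model. The documents do not support that. They give no shift or prevalence from which to size the reverse path, and their own 2.7 for poor health favours a forward path as well.

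**Conclusion.** The point holds in a limited form. As written, the plan cannot support *determinants*, *influencing* or *affecting* for general health and carrying difficulty, because it does not place them before the accident and its Introduction describes the reverse path. It is also inconsistent with itself, since the abstract's aim is associational. The gap in the text is certain; the size of any bias is unknown. With no forward effect, shifts of 2% to 20% and baselines of 20% to 60%, all assumed, the apparent odds ratio runs from 1.03 to 2.25. This concerns what may be concluded; it is not a reason to discard the planned model. The change should be made before results are written.

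**What to change.** 1. Replace *determinants* (title), *influencing* (abstract Methods and section 2.4) and *risk factors affecting* (end of the Introduction) with *factors associated with*. The motivation sentence in the Introduction and the literature-selection sentence in section 2.3 can stay.
2. Check the survey's question wording. If it dates general health and carrying difficulty before the accident, give that reference period in section 2.3. If not, state that both are correlates that may partly follow the accident.
3. Keep the full model as primary. Add one fixed sensitivity model, the same survey-weighted logistic regression without exactly these two variables, and report its odds ratios beside the primary ones.
4. State in section 2.4 that this comparison shows only how far the other odds ratios depend on the two variables. It gives no estimate for them, is confounded if they predate the accident, and cannot distinguish reverse causation from confounding or mediation.

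The cost is one extra regression on the same data, one more results column and weaker claims.
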